- h) Treatment with plasmapheresis within 4 weeks prior to randomization.
- i) Subjects who have received a live / attenuated vaccine within 30 days of first treatment.

4. Physical and Laboratory Test Findings

Screening Laboratory evaluations within the following parameters:

- a) Absolute neutrophil count (ANC) $< 1,000$ cells/ μ L (1.0×10^9 /L) (Growth factors cannot be used within 1 week of first drug administration. No pegylated growth factors within 3 weeks of first drug administration)
- b) Platelet count $< 75,000$ cells/ μ L (75×10^9 /L) ($< 30 \times 10^9$ /L if $\geq 50\%$ of bone marrow nucleated cells were plasma cells). Qualifying laboratory value must occur at most recent measurement prior to study entry. No transfusions are allowed within 72 hours prior to qualifying laboratory value
- c) Hemoglobin < 8 g/dl (No transfusions are allowed within 72 hours prior to qualifying laboratory value)
- d) Total Bilirubin $> 1.5 \times$ upper limit of normal (ULN) (except subjects with Gilbert Syndrome, who can have total bilirubin up to $3.0 \times$ ULN)
- e) AST (SGOT) and ALT (SGPT) $> 3.0 \times$ ULN

f) Renal function: Estimated creatinine clearance by Cockcroft-Gault formula $< 30 \text{ mL/min}$

- $\text{Female CrCl} = (140 - \text{age in years}) \times \text{weight in kg} \times 0.85$
72 x serum creatinine in mg/dl
- $\text{Male CrCl} = (140 - \text{age in years}) \times \text{weight in kg} \times 1.00$
72 x serum creatinine in mg/dl

g) Corrected serum calcium $\geq 11.5 \text{ mg/dl}$ within 2 weeks of initiation of study drug (despite appropriate measures such a short course of steroids, bisphosphonates, hydration, calcitonin)

5. Allergies and Adverse Drug Reaction

- a) History of allergy or hypersensitivity to study drug components
- b) History of severe hypersensitivity reaction to any monoclonal antibody

6. Other Exclusion Criteria

- a) Prisoners or subjects who are involuntarily incarcerated. (Note: under certain specific circumstances a person who has been imprisoned may be included or permitted to continue as a subject. Strict conditions apply and Bristol-Myers Squibb approval is required)
- b) Subjects who are compulsorily detained for treatment of either a psychiatric or physical (eg, infectious disease) illness

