6 ADVERSE EVENTS

An *Adverse Event (AE)* is defined as any new untoward medical occurrence or worsening of a preexisting medical condition in a clinical investigation subject administered study drug and that does not necessarily have a causal relationship with this treatment. An AE can therefore be any

unfavorable and unintended sign (such as an abnormal laboratory finding), symptom, or disease temporally associated with the use of study drug, whether or not considered related to the study drug.

The causal relationship to study drug is determined by a physician and should be used to assess all adverse events (AE). The causal relationship can be one of the following:

Related: There is a reasonable causal relationship between study drug administration and the AE.

Not related: There is not a reasonable causal relationship between study drug administration and the AE.

The term "reasonable causal relationship" means there is evidence to suggest a causal relationship.

Adverse events can be spontaneously reported or elicited during open-ended questioning, examination, or evaluation of a subject. (In order to prevent reporting bias, subjects should not be questioned regarding the specific occurrence of one or more AEs.)

BMS will be reporting adverse events to regulatory authorities and ethics committees according to local applicable laws including European Directive 2001/20/EC and FDA Code of Federal Regulations 21 CFR Parts 312 and 320.

6.1 **Serious Adverse Events**

A **Serious Adverse Event (SAE)** is any untoward medical occurrence that at any dose:

- results in death
- is life-threatening (defined as an event in which the subject was at risk of death at the time of the event; it does not refer to an event which hypothetically might have caused death if it were more severe)
- requires inpatient hospitalization or causes prolongation of existing hospitalization (see NOTE below)
- results in persistent or significant disability/incapacity
- is a congenital anomaly/birth defect

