8.4.3 Safety Analyses

The safety analysis will be performed in all treated subjects. Descriptive statistics of safety will be presented using National Cancer Institute (NCI) Common Terminology Criteria for Adverse Events (CTCAE) version 4.0 by treatment group. Adverse Events (AE), drug-related AEs, Serious Adverse Events (SAE) and drug-related SAEs will be tabulated using worst grade per NCI CTCAE v.4.0 criteria by system organ class and preferred term. On-study lab parameters including hematology, chemistry, liver function and renal function will be summarized using worst grade per NCI CTCAE v.4.0 criteria.

8.4.7 *Other Analyses*

Not applicable

8.5 *Interim Analyses*

Interim Analysis for PFS Futility

At FDA's request on 21-June-2018, a formal PFS interim analysis for futility was conducted in August 2018 based on the database lock on 12-April-2018. The investigator assessed progression events (NPd and Pd arms) were used in this analysis. Prior to running the futility analysis, a futility criteria was defined based on conditional power assuming 85 events (30% information fraction). The stopping criteria for futility was that the conditional power under observed trend is strictly less than 1%. This would correspond to a HR (NPd vs. Pd) boundary of 0.995 and the corresponding conditional power under alternative would be 67.8%, ie if alternative hypothesis is true (HR = 0.667), there is still 67.8% chance that the study will be positive at the final analysis.

Subsequently, after conducting the interim analysis, the decision was made to permanently discontinue enrolment based on insufficient clinical benefit observed at an interim futility analysis for PFS. All futility analyses were conducted by the unblinded independent statistics vendor.

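### Section 8.4.3 reports laboratory values by worst on-study grade alone, so abnormalities present at entry cannot be told apart from those that arise on treatment

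*Combined protocol and SAP*

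**What the plan says.** **Entry limits.** Section 3.3.2, item 4, excludes a neutrophil count below 1.0 × 10⁹/L, hemoglobin below 8 g/dL, estimated creatinine clearance below 30 mL/min, AST and ALT above 3 × ULN, and total bilirubin above 1.5 × ULN (up to 3 × ULN is accepted in Gilbert syndrome). The platelet limit is 75 × 10⁹/L, falling to 30 × 10⁹/L where at least 50% "of bone marrow nucleated cells were plasma cells". For platelets it adds: "Qualifying laboratory value must occur at most recent measurement prior to study entry". Lymphocytes have no limit. Values short of normal are thus admitted for several parameters.

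**Laboratory summary.** Section 8.4.3 states: "On-study lab parameters including hematology, chemistry, liver function and renal function will be summarized using worst grade per NCI CTCAE v.4.0 criteria". The population is all treated subjects and the presentation is by arm: "Descriptive statistics of safety will be presented using National Cancer Institute (NCI) Common Terminology Criteria for Adverse Events (CTCAE) version 4.0 by treatment group". It names no baseline value, shift from baseline or rule for worsening.

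**Adverse events.** Section 6 defines an adverse event as "any new untoward medical occurrence or worsening of a preexisting medical condition". Section 6.3 puts a laboratory abnormality on the AE form only if it is clinically significant or serious, leads to interruption or discontinuation of drug, or needs specific corrective treatment.

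**Data available.** Table 5.1-1 requires a blood count and serum chemistry within 14 days of randomization. Section 8.4.1 plans a baseline summary by arm but does not mention laboratory grades.

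**The concern.** The laboratory table is meant to show what happened to blood counts, liver tests and renal function during the study. With worst grade alone, a subject who enters with a low count and stays there is shown in the same cell as a subject who entered with a normal count and fell to that grade. The reader cannot separate the two, and no other planned table is stated to do so. The AE tables require something new or worse, but Section 6.3 restricts which laboratory findings reach them, so they do not give a full grade-level picture.

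At stake is how the laboratory rates in each arm are read: absolute rates look higher than the rate of new or worsened abnormality, and a real difference between N-Pd and Pd looks somewhat smaller. Assessing safety and tolerability is an exploratory objective (Section 1.5.3).

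**Working it through.** The plan states no figure on this point, so there is nothing to reproduce. The steps below show the direction and possible size of the effect.

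**Inputs.**
- t, the true rate of reaching a given grade on study among subjects not already there. Illustrative values are 22% and 48%, the Grade 3–4 thrombocytopenia and neutropenia figures that Section 1.3.3 cites for pomalidomide plus low-dose dexamethasone. Those are adverse event rates from another trial and serve only as a scale.
- p0, the share already at that grade at entry. It is not in the documents; the assumed range is 2% to 30%.
- Arm sizes of 75 (N-Pd) and 71 (Pd), from Section 3.1. These are randomized counts; the safety tables use treated subjects.

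**Step 1: rate shown.** If every subject at the grade at entry also shows it on study, the table shows p0 + (1 − p0) × t. For p0 = 10% and t = 22%: 0.10 + 0.90 × 0.22 = 0.298.

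**Step 2: difference shown.** If p0 is the same in both arms, it cancels and a true difference d is shown as (1 − p0) × d. For d = 10 points and p0 = 10%: 0.90 × 10 = 9.0.

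| p0 (assumed) | true 22% shown as | true 48% shown as | true 10-point difference shown as |
|---|---|---|---|
| 2% | 23.6% | 49.0% | 9.8 |
| 5% | 25.9% | 50.6% | 9.5 |
| 10% | 29.8% | 53.2% | 9.0 |
| 20% | 37.6% | 58.4% | 8.0 |
| 30% | 45.4% | 63.6% | 7.0 |

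**Step 3: persistence.** If only a share s of those at the grade at entry show it on study, the rate shown is p0 × s + (1 − p0) × t, and the inflation is p0 × (s − t). The table above takes s = 1, its upper limit.

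**Step 4: chance imbalance at entry.** Write r for the rate shown in Step 1. Its variance per subject splits as r(1 − r) = (1 − t)² p0(1 − p0) + (1 − p0) t(1 − t). At t = 22% and p0 = 5%: 0.0289 + 0.1630 = 0.1919. The first term, multiplied by (1/75 + 1/71), gives the SD of the arm difference due to baseline imbalance: 2.8, 3.9 and 5.2 points at p0 = 5%, 10% and 20%. The total SD of the arm difference is √[r(1 − r)(1/75 + 1/71)]: 7.3, 7.6 and 8.0 points, against 6.9 points at r = 22% with no baseline cases. The net increase is about 0.4, 0.7 and 1.2 points.

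**The case against.** **The table attributes nothing to drug.** A reader might infer that pre-existing cytopenias will be counted as treatment toxicity. The documents do not support that. Section 8.4.3 calls these on-study parameters and describes them by arm. AEs and drug-related AEs are tabulated separately, and the Section 6 definition excludes an unchanged pre-existing condition. This stands; what remains is that the table cannot distinguish the two sources.

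**Randomization protects the comparison.** A reader might also infer that the N-Pd versus Pd comparison is biased. It is not biased toward either arm: p0 is equal in expectation, so only dilution and chance imbalance remain. Nor should the 2.8 to 5.2 points in Step 4 be read as error added on top of ordinary sampling variation; they are one component of it, and the net increase is about 1 point or less.

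**Large values of p0 are unsupported.** For thrombocytopenia, any entry count from 30 to below 75 × 10⁹/L is open only to subjects with at least 50% marrow plasma cells, and nothing in the documents suggests that 20% of subjects would enter at Grade 3–4. The CTCAE cut-points are not printed either, so the entry limits cannot be translated into grades from the text. This stands: the upper rows of the table show arithmetic, not expectation.

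**A separate SAP may contain shift tables.** The supplied text includes none, so absence is shown for the protocol only. But Sections 8.4.2.2 and 8.4.2.3 expressly leave detail to the SAP, whereas Section 8.4.3 does not: it states its own rule, worst grade. The objection limits the certainty of the point without removing it.

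**Conclusion.** The point holds as a minor reporting weakness. Given the entry limits in Section 3.3.2, the rule in Section 8.4.3 mixes abnormalities present at entry with those that arise on treatment. Absolute worst-grade rates are overstated by up to p0 × (1 − t): 3.9 points at p0 = 5% and t = 22%, and 15.6 points at p0 = 20%, which is probably too high for Grade 3–4 thrombocytopenia. A 10-point difference between arms loses 0.5 to 2 points over the same range.

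These sizes rest on an assumed p0, on persistence of the entry grade, and on borrowed AE rates. The direction follows from the rule itself wherever subjects at the grade on entry are more likely to show it on study than the others (s greater than t). The AE tables, the primary PFS analysis and every stated figure in the plan are unaffected.

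**What to change.** In Section 8.4.3:

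- Define the laboratory baseline as the last value before first dose, and count only later values as on-study. This matters because Table 5.1-2 lets the Cycle 1 Day 1 blood count be drawn up to 3 days before dosing, and the section does not say on which side of the line it falls.
- Present tables by arm of baseline grade against worst on-study grade for each graded parameter.
- Count subjects whose worst grade exceeds their baseline grade. For a threshold such as Grade 3 or higher, also give the rate among subjects below the threshold at baseline. With all treated subjects as denominator, the worsening rate is (1 − p0) × t, for example 0.90 × 22% = 19.8%, so the 1 − p0 dilution of the arm difference would remain.
- Keep the plain worst-grade table alongside.

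No new data are needed, because screening blood counts and chemistry are already collected. Section 8.4 places the main analysis after the last subject's safety follow-up, so the rule can be written before then. The cost is a few sentences, one more set of standard tables, and lower headline rates that need a short explanation next to the plain table.

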3.4 Concomitant Treatments

3.4.1 Prohibited and/or Restricted Treatments

Any systemic, anti-myeloma therapy other than the study drugs is prohibited while on study therapy. Concomitant steroids, other than weekly dexamethasone or steroids allowed (as defined in eligibility criteria) are prohibited unless used to treat an adverse event. Guidelines for selection and use of other concomitant medications should be derived from the pomalidomide and dexamethasone prescribing information.

Avoid co-administration of pomalidomide with strong inhibitors of CYP1A2 unless medically necessary. Co-administration of pomalidomide with drugs that are strong inhibitors of CYP1A2 (eg, ciprofloxacin, enoxacin and fluvoxamine) and CYP3A4/5 (eg, ketoconazole) or P-gp could increase pomalidomide exposure and should be avoided, unless medically necessary^{28, 29}. The FDA DDI database link is the following:

<http://www.fda.gov/Drugs/DevelopmentApprovalProcess/DevelopmentResources/DrugInteractionsLabeling/ucm093664.htm>

Other than study medications, administration of any therapeutic or diagnostic investigational agent (for any indication) is prohibited while on study therapy without prior Sponsor approval.

Immunosuppressive agents are prohibited (unless utilized to treat drug-related adverse events).

Any live / attenuated vaccine (eg varicella, zoster, yellow fever, rotavirus, oral polio and measles, mumps, rubella (MMR)) is prohibited during treatment and until 100 days post last dose.

3.4.2 Required Treatment

Subjects must receive thrombo-embolic prophylaxis, per institutional guidelines or PI discretion. Examples of commonly used thrombo-embolic prophylaxis medications include aspirin, low molecular weight heparin, and vitamin K antagonists.

Subjects must receive pre-medications ([Sections 4.5.1.3.6](#) and [4.5.1.3.7](#)) prior to each dose of elotuzumab.

3.4.3 Permitted at Investigator's Discretion

IV corticosteroids, diphenhydramine, or hydroxyzine, acetaminophen/ paracetamol, H2 inhibitors (ie, cimetidine), leukotriene inhibitors (montelukast sodium) for the management of infusion reactions. Additional supportive measures should be provided as indicated including:

- oxygen inhalation
- epinephrine
- bronchodilators
- oral antiviral and antimicrobial prophylaxis

- anti-emetics
- bisphosphonates

Subjects are permitted the use of topical, ocular, intra-articular, intranasal, and inhalational corticosteroids (with minimal systemic absorption). Adrenal replacement steroid doses > 10 mg daily prednisone are permitted. A brief (less than 3 weeks) course of corticosteroids for prophylaxis (eg, contrast dye allergy) or for treatment of non-autoimmune conditions (eg, delayed-type hypersensitivity reaction caused by a contact allergen) is permitted

Per the ASCO 2007 Clinical Practice Guidelines³⁰, bisphosphonate therapy should be administered for a period of 2 years. At 2 years, the investigator should seriously consider discontinuing bisphosphonates in subjects with at least stable disease, although further use is at the discretion of the investigator.

Routine clinical practice for monitoring and prevention of osteonecrosis of the jaw (ie, comprehensive dental exam, treating active oral infections, eliminating sites of high risks for oral infection, excellent oral hygiene and avoiding invasive dental procedures while on treatment) must be followed.

- Erythropoietin (EPO) or erythropoiesis stimulating agents (prior and ongoing use according to the package insert and institutional guidelines)
- Red blood cell or platelet transfusion
- Prophylactic administration of G-CSF for neutropenic subjects or therapeutic use in subjects with serious neutropenic complications (such as tissue infection, sepsis syndrome or fungal infection) may be considered at the investigator's discretion, consistent with American Society of Clinical Oncology guidelines (American Society of Clinical Oncology 2006).

3.4.4 *Surgery and Radiation*

Use of radiotherapy or surgical intervention must be recorded on the appropriate Case Report Form.

Localized radiation therapy to a site of pre-existing disease may be permitted while on study. Following approval by the medical monitor, the subject may continue with protocol therapy without interruption during the course of palliative radiation therapy if the investigator believes that the risk of excessive bone marrow suppression or other toxicity is acceptable, and it is in the best interest of the subject to do so.

If the subject develops a definite increase in the size of existing bone lesions or soft tissue plasmacytomas that meets the criteria for disease progression (see [Appendix 3](#)) treatment must be discontinued for progressive disease regardless of whether radiation therapy is initiated ([Section 3.5](#)).

Kyphoplasty, vertebroplasty, or emergency orthopedic surgery is permitted.

3.5 Discontinuation of Subjects following any Treatment with Study Drug

Subjects MUST discontinue investigational product (and non-investigational product at the discretion of the investigator) for any of the following reasons:

- Subject's request to stop study treatment
- Progressive Disease according to IMWG criteria
- Any clinical adverse event (AE), laboratory abnormality or intercurrent illness which, in the opinion of the investigator, indicates that continued participation in the study is not in the best interest of the subject
- Termination of the study by Bristol-Myers Squibb (BMS)
- Loss of ability to freely provide consent through imprisonment or involuntarily incarceration for treatment of either a psychiatric or physical (eg, infectious disease) illness
- Subjects who receive any non-protocol specified systemic anti-myeloma therapy before documented progression will be discontinued from all study treatment (including pomalidomide and dexamethasone); however, tumor assessments will continue at 4 week intervals until documented progression.
- Subjects experiencing a Grade 4 infusion reaction related to elotuzumab must discontinue elotuzumab only. Subjects may continue nivolumab, pomalidomide and dexamethasone treatment. Refer to [Section 4.5.4](#).
- Subjects experiencing angioedema, Grade 4 rash, exfoliative or bullous rash, Stevens Johnson syndrome, or toxic epidermal necrolysis must discontinue pomalidomide and nivolumab. Subjects may continue on elotuzumab and dexamethasone.
- Subjects experiencing a 56 day delay in all study drugs (nivolumab, pomalidomide, dexamethasone, and elotuzumab) due to an adverse event(s) related to study treatment must be discontinued from study drug. Subjects experiencing delays unrelated to study therapy, for example due to radiation therapy, may delay study treatment up to 84 days. Further delays may be allowed after discussion with the BMS Medical Monitor.
- Subjects experiencing a Grade 3 or 4 infusion reaction related to nivolumab must discontinue nivolumab only. Subjects may continue elotuzumab, pomalidomide and dexamethasone treatment. Refer to Section 4.5.4 for additional reasons to discontinue nivolumab dosing permanently.

In the case of pregnancy, the investigator must immediately notify the BMS Medical Monitor/designee of this event *and treatment with the IMPs would immediately be stopped*. In most cases, the study drug will be permanently discontinued in an appropriate manner. Please call the BMS Medical Monitor within 24 hours of awareness of the pregnancy. If the investigator determines a possible favorable benefit/risk ratio that warrants continuation of study drug (*ie, allowing restart of study drug if patient chose to terminate the pregnancy*), a discussion between the investigator and the BMS Medical Monitor/designee must occur *so permission can be granted*.

All subjects who discontinue study drug should comply with protocol specified follow-up procedures as outlined in [Section 5](#). The only exception to this requirement is when a subject withdraws consent for all study procedures including post-treatment study follow-up or loses the

ability to consent freely (ie, is imprisoned or involuntarily incarcerated for the treatment of either a psychiatric or physical illness).

If study drug is discontinued prior to the subject's completion of the study, the reason for the discontinuation must be documented in the subject's medical records and entered on the appropriate case report form (CRF) page.

3.6 Post Study Drug Study Follow up

PFS and OS are key endpoints of the study. Post treatment study follow-up is essential to preserving subject safety and the integrity of the study. Subjects who discontinue study treatment prior to progression must continue to be followed for collection of protocol-defined PFS. Subjects who discontinue study therapy must also continue to be followed for overall survival data until death or the conclusion of the study.

BMS may request that survival data be collected on all treated/randomized subjects outside of the protocol defined window, [Table 5.1-3](#). At the time of this request, each subject will be contacted to determine their survival status unless the subject has withdrawn consent for all contacts or is lost to follow-up.

3.6.1 Withdrawal of Consent

Subjects who request to discontinue study drug will remain in the study and must continue to be followed for protocol specified follow-up procedures. The only exception to this is when a subject specifically withdraws consent for any further contact with him/her or persons previously authorized by subject to provide this information. Subjects should notify the investigator of the decision to withdraw consent from future follow-up **in writing**, whenever possible. The withdrawal of consent should be explained in detail in the medical records by the investigator, as to whether the withdrawal is from further treatment with study drug only or also from study procedures and/or post treatment study follow-up, and entered on the appropriate CRF page. In the event that vital status (whether the subject is alive or dead) is being measured, publicly available information should be used to determine vital status only as appropriately directed in accordance with local law.

